## 7. SAFETY MEASUREMENTS

### 7.1. Collecting, Recording and Reporting of Adverse Events

Adverse events are not likely during a study of ultrasound, given the very low risk of fetal effects during anatomy ultrasound (19-23). Fetuses of mothers in the intervention arm will be evaluated by the gold standard (GSS) in the second trimester, in order to rule out any missed anomalies. Fetuses in both arms are exposed to similar amounts of ultrasound time (all fetuses have at least two ultrasounds in the first trimester and one in the second trimester).

Intervention arm total number of scans:

1. Screening ultrasound (estimated time 2 minutes)
2. First trimester anatomy ultrasound (estimated time 25 minutes)
3. Scheduled limited first trimester ultrasound (estimated time 10 minutes)
4. GSS in second trimester to ensure standard of care is met (estimated time 45 minutes)

Comparison arm total number of scans:

1. Screening ultrasound (estimated time 2 minutes)
2. Scheduled limited first trimester ultrasound (estimated time 10 minutes)
3. Second trimester anatomy ultrasound (estimated time 30 minutes)

Multiple ultrasounds are common in this population.

Maternal adverse effects including discomfort will be noted in the study database but will not be reported to a study safety monitor.

## **7.2. Safety Monitoring Plan**

The research ultrasound will be stored locally on an E8 machine or on a hard drive owned and protected by UT. It will not be available in the medical record. Data regarding ultrasound (length in minutes, date, gestational age, findings) will be stored in RedCap. Maternal and neonatal outcomes will be collected from Care4 or Epic (depending on the location of delivery) and stored in RedCap.

Adverse effects are not expected from an ultrasound intervention, although discomfort especially with transvaginal ultrasound is frequently reported by patients. In the case of patient discomfort with the ultrasound exam, the exam will be paused and the patient asked for permission to continue. If the patient declines the continuation of the exam, the exam will stop and completion will be assessed based on the images obtained before that point.

## **8. DATA ANALYSIS**

### **8.1. Data Quality Assurance**

Data will be checked by at least two members of the research team for integrity. The entire study team (CB, EH, BS) will have access to study documents in RedCap and to ultrasound images on the protected UT drive (encrypted and kept in a locked office in the Medical School Building at the medical center campus). A linking log will be used to limit spread of PHI into the RedCap record, so that inadvertent download of data does not compromise patient confidentiality and anonymity. This linking log will be kept in the same system as the data but will not be accessible with the dataset or ultrasound images, in order to protect patient identifying variables as much as possible.

### **8.2. Data Entry and Storage**

Data will be entered directly by patients into RedCap with research staff supervision (for demographics) or independently (for survey replies), or by the research staff. A linking log will be used. The linking log and images will be destroyed at the close of the study (upon publication). De-identified records will be retained for 5 years and made available upon academic request to the corresponding author.

## **9.2. Statistical and Analytical Plans**

Analysis will be carried out according to the intention-to-treat principle. All randomized subjects will be included in analyses for which they have data. Frequentist statistics will be reported, including mean number of scans in each group (compared with t tests, with ANOVA between classes of obesity), the proportion of complete scans in each group (compared with chi square test), and the mean total scan time (t tests). Secondary outcomes will also be analysed with a frequentist approach. Descriptive statistics will also be provided about anomalies found and missed (anticipated to be low, so likely few significant findings to report). In addition, patient perspectives will be described.

# **10. ETHICAL CONSIDERATIONS**

## **10.1. Informed Consent**

Informed consent will be obtained in either English or Spanish and will preferably be performed by e-consenting (no paper copy of the consent). Patients will consent via a tablet or mobile device directly into RedCap and will be provided with an emailed copy of their consent form.

## **10.2. IRB review**

A copy of the protocol will be submitted to the Institutional Review Board (IRB) for written approval. The Principal Investigator will obtain approval from the IRB for all subsequent protocol amendments.

## **10.3. Confidentiality of Data and Patient Records**

Subject confidentiality will be maintained and all records will be securely stored.

## 11. PUBLICATIONS

We anticipate three primary publications coming out of this study. Completion rates and multiple second outcomes can be published in journals of maternal-fetal medicine or ultrasound.

## 12. RETENTION OF TRIAL DOCUMENTS

All records, including all source documentation (containing evidence to study eligibility, history and physical findings, laboratory data, etc) as well as IRB records and regulatory documents will be retained by the PI in a secure storage facility. The records will be accessible for inspection and copying by authorized authorities.

## List of Attachments

**Appendix 1      Questionnaires used in the Trial**

**Appendix 2      Consent Form**

## Appendix 3      Standardized Patient Emails

## APPENDIX 1

### Patient survey after detailed anatomy ultrasound for EASE-O

Version 1.0, last revised 8/2/20

This survey is 12 questions long and should take about 15 minutes.

Recently, you had a “[first/second] trimester detailed anatomy ultrasound,” or an ultrasound that looked at the body parts of your baby in detail at [12-14/18-22] weeks. These questions will ask you about your experience with your ultrasound and your opinions about finding birth defects early in pregnancy.

1. Overall, how satisfied were you with today's ultrasound?
  - a. Very satisfied
  - b. Somewhat satisfied
  - c. Neither satisfied nor dissatisfied
  - d. Somewhat dissatisfied
  - e. Very dissatisfied
  
2. How would you rate the level of discomfort required by this ultrasound?
  - a. Very comfortable
  - b. Somewhat comfortable
  - c. Neither comfortable nor uncomfortable
  - d. Somewhat uncomfortable
  - e. Very uncomfortable
  
3. How would you rate the length of time it took to complete this ultrasound? Don't count the time it took to do other things, like park or wait in the waiting room.
  - a. Much longer than I expected
  - b. A little longer than I expected
  - c. About the time I expected
  - d. A little shorter than I expected
  - e. Much shorter than I expected
  
4. How satisfied are you with the length of time it took to complete this ultrasound? Don't count the time it took to do other things, like park or wait in the waiting room.
  - a. Very satisfied
  - b. Somewhat satisfied
  - c. Neither satisfied nor dissatisfied
  - d. Somewhat dissatisfied
  - e. Very dissatisfied
  
5. How likely are you to recommend [first/second] trimester anatomy screening to other pregnant women?
  - a. Very likely
  - b. Somewhat unlikely
  - c. Neither likely nor unlikely
  - d. Somewhat unlikely

e. Very unlikely

The next questions ask for your opinions on finding out about birth defects early. Most birth defects are discovered at 18-22 weeks, but EASE-O is studying ultrasounds which can discover many of the same birth defects at 12-14 weeks. For this section, remember that:

- Finding out about a birth defect early can lead to more ultrasounds and testing
- Finding out about a birth defect early means a longer time knowing about the problem, when there may be no therapy for the fetus until birth
- Abortion (ending a pregnancy before birth) is safer for the woman when done earlier in pregnancy

6. For you, how important is finding out about any birth defects early in your pregnancy?
  - a. Very important
  - b. Important
  - c. Fairly important
  - d. Slightly important
  - e. Not important
7. How much testing would you seek if an abnormal ultrasound finding was discovered during your detailed scan?
  - a. All available testing, even invasive options
  - b. Some available testing, only invasive options if highly recommended
  - c. Some available testing, but not invasive options
  - d. Very little testing, definitely no invasive options
  - e. No testing at all, even if recommended
8. If there was a therapy or surgery that you could undergo during pregnancy for a birth defect discovered in your fetus, how likely would you be to agree to it?
  - a. Very likely
  - b. Somewhat unlikely
  - c. Neither likely nor unlikely
  - d. Somewhat unlikely
  - e. Very unlikely
9. Some women in this study got an ultrasound at [18 to 22/12 to 14] weeks instead of when you got your ultrasound. Please tell us whether you agree or disagree with the following statement: "I wish I could have been in the other group, and gotten my detailed anatomy ultrasound at [18 to 22/12 to 14] weeks."
  - a. Strongly agree
  - b. Agree
  - c. Neither agree nor disagree
  - d. Disagree
  - e. Strongly disagree

10. You got your detailed anatomy ultrasound at [12-14/18-22] weeks. If given the choice in another pregnancy (even if another baby is not your plan), how likely are you to choose the same timing again?

- a. Very likely
- b. Somewhat likely
- c. Neither likely nor unlikely
- d. Somewhat unlikely
- e. Very unlikely

The last two questions involve questions about abortion. These questions may be sensitive and you may skip them. If you can answer them, you help us understand how women feel about issues that affect early diagnosis of birth defects.

[SKIP ENTIRE SECTION]

11. Some birth defects are very serious and limit the fetus' length of life and/or future quality of life. In certain cases, abortion is offered as an option. What are your feelings on abortion (ending a pregnancy before birth) in general?

- a. Very supportive of abortion
- b. Somewhat supportive of abortion
- c. Neither supportive nor opposed to abortion
- d. Somewhat opposed to abortion
- e. Very opposed to abortion
- f. [SKIP THIS QUESTION]

12. Imagine that you were pregnant with a fetus with a very serious birth defect, that limited the fetus' length of life and/or future quality of life. If your doctor offered abortion as an option, how likely would you be to seek an abortion for yourself?

- a. Very likely
- b. Somewhat likely
- c. Neither likely nor unlikely
- d. Somewhat unlikely
- e. Very unlikely
- f. [SKIP THIS QUESTION]

Thank you for your participation! This survey helps us understand how you feel about when you get your ultrasound and what you want to do with the information.

Autopopulated fields:

[Study ID]

[Survey completion date]

[EDD]

[Gestational age at survey completion]

[Group: intervention/comparison]

[Primary outcome (initial anatomy scan complete?): Y/N]

## APPENDIX 2

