### **2.5. Secondary Outcome**

Secondary outcomes include:

1. Completion rate of both first and second trimester scans (when considered as a single instrument to visualize the fetal anatomy, what is the rate of complete visualization divided by all women?)
2. Total length of scanning time in the first trimester ultrasound group
3. Number of anomalies identified (and missed) in each group
4. Neonatal outcomes (survival, gestational age at delivery, NICU admission, hospital LOS, neonatal morbidities including respiratory distress syndrome, transient tachypnea of the newborn, intraventricular haemorrhage, necrotizing enterocolitis)
5. Patient feedback to standardized surveys (see attached)

6. Cost of intervention compared to usual care (cost benefit analysis based on whether more ultrasounds were done in cases of early discovery of anomalies)

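### Survey questions 5 and 8 print 'Somewhat unlikely' twice and omit 'Somewhat likely', so answer b cannot be interpreted and the moderately positive category is lost for these two items

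*Combined protocol and SAP*

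**What the plan says.** Section 2.5 names patient feedback from the attached standardized surveys as the fifth of six secondary outcomes. Section 9.2 plans a frequentist analysis of secondary outcomes in general. On this material specifically it says only: "In addition, patient perspectives will be described".

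Appendix 1 contains the 12-question survey, marked version 1.0 and last revised 8/2/20. Four of its questions use a five-step 'how likely' scale:

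- Question 5: "How likely are you to recommend [first/second] trimester anatomy screening to other pregnant women"
- Question 8, on a therapy or surgery for a birth defect found in the fetus: "how likely would you be to agree to it"
- Question 10, on choosing the same timing in another pregnancy
- Question 12, on seeking an abortion after a very serious diagnosis (with an added skip option)

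In questions 5 and 8 the second option is "b. Somewhat unlikely" and the fourth is "d. Somewhat unlikely". In questions 10 and 12 the second option is "b. Somewhat likely".

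**The concern.** A five-step likelihood scale needs a moderate option on each side of the neutral point. In questions 5 and 8 the moderate positive is replaced by a second copy of the moderate negative. A woman who is somewhat likely to recommend the scan must overstate (a), understate (c), or choose b because of where it sits, against what it says. Another woman may choose b because of what it says. The data set records the same answer for both.

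At stake is the part of a named secondary outcome that these two questions supply. Question 5 is the only item on recommending the assigned timing, and it is put to both arms. No one is present to clarify: Section 4.3 sends the survey by email, and Section 8.2 has patients enter their replies independently.

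**Working it through.** The plan states no figure here, so the check compares the printed options.

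| Position | Questions 5 and 8 | Questions 10 and 12 |
|---|---|---|
| a | strong positive | strong positive |
| b | "b. Somewhat unlikely" | "b. Somewhat likely" |
| c | neutral | neutral |
| d | "d. Somewhat unlikely" | "d. Somewhat unlikely" |
| e | strong negative | strong negative |

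**Count of labels.** Questions 5 and 8 each have 5 positions but 4 distinct labels: 1 positive, 1 neutral, and 2 negative labels filling 3 positions. Questions 10 and 12 each have 5 distinct scale labels: 2 positive, 1 neutral, 2 negative. The error affects 2 of the 4 'how likely' questions and 2 of the 12 questions overall.

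**Error or artefact.** The same whole-word substitution occurs at the same position in two questions, while the parallel questions read correctly. A fault in reading the PDF is an unlikely cause. An identical label on both sides of neutral has no evident design purpose.

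**Effect on a summary.** Let n be the number of respondents in an arm, and n_a and n_b the numbers choosing a and b.

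- b read by position, as positive: share likely = (n_a + n_b)/n
- b read by wording, as negative: share likely = n_a/n
- Difference = n_b/n

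The summary is therefore uncertain by the whole share of b answers. Section 4.1 gives 19 + 20 + 20 = 59 women per arm. If all reply, each b answer is worth 1/59 = 1.7 percentage points. The documents give no basis for predicting n_b.

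These two codings do not capture all of the distortion. Somewhat likely women who moved to a or c are counted there and cannot be identified. The labels a, c and e keep their meaning, but the counts at a and c may include displaced answers.

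**The case against.** The strongest reply is that little depends on these two items. The survey is the fifth of six secondary outcomes and its reporting is mainly descriptive. No sample size, safety measure or decision rule uses it. Section 4.3 describes the survey as being about satisfaction with the technique, which questions 1 and 4 ask on intact scales. Preference between timings is asked most directly by questions 9 and 10, also intact. Question 8 concerns a hypothetical therapy rather than the scan received. All of this stands and limits the consequence. It does not make b interpretable.

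Three stronger readings are tempting, and the documents do not support them.

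- *Willingness to recommend or to accept therapy cannot be measured at all.* Options a, c and e still carry information. What is lost is the moderately positive category and the meaning of b.
- *Question 5 is the main acceptability item.* No survey item is given that status.
- *The result could move by 20 to 40 points.* This assumes that 20–40% of women are somewhat likely (0.20 × 59 ≈ 12 to 0.40 × 59 ≈ 24 per arm), that all of them choose b, and that every woman replies. No document figure supports the percentage, and some of these women would choose a or c. It is a ceiling on an assumed input.

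A further limit is that the RedCap form actually fielded is not shown. Spanish speakers are eligible under Section 3.3, but no Spanish survey appears. Appendix 1 is listed as the questionnaires used in the trial, so the error may well be live, but this needs checking.

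**Conclusion.** The point holds in a limited form. As printed, questions 5 and 8 cannot give a valid five-point score or a 'very or somewhat likely' proportion, because b is ambiguous and the moderately positive option is missing. The size is 2 of 12 questions within one secondary outcome, with uncertainty in each affected proportion equal to the share of respondents choosing b. The other ten questions' response options and the primary outcome are not touched.

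The effect on collected data rests on one assumption, that the fielded form matches Appendix 1. The number of answers already affected is unknown. Section 4 schedules recruitment from September 2020 to June 2021 and the protocol carries an IRB approval date of 08/12/2021, so it should not be presumed small.

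**What to change.** 1. Check option b of questions 5 and 8 in the live RedCap form and in any Spanish version.
2. Where the error is present, change option b to *Somewhat likely*, matching questions 10 and 12, and issue a new survey version with its own number and date.
3. For surveys completed on the faulty form, re-ask the two items where possible. Responses carry a study ID, but Section 8.2 has the linking log destroyed upon publication, so this must be done before then.
4. Where re-asking fails, report all raw categories by survey version, flag b as ambiguous, and show the result with b coded each way. State that displaced answers at a and c cannot be recovered.
5. Do not set d to missing. It is correctly labelled and placed, and removing it would selectively delete negative answers and make both timings look better.

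The cost is one word in each of two questions, a minor IRB amendment, and the effort of recontact. Re-asked answers come later than planned and should be marked as such. Ambiguous b answers already collected will remain wherever re-asking fails.

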### Standardized Emails for EASE-O

Version 1.0, last revised 8/2/20

#### Standardized Welcome Email

Dear [Name],

Thank you for participating in EASE-O, a randomized clinical trial to find out when is the best time for a detailed anatomy ultrasound in women with a BMI of 35 or greater. We're so glad you're part of the study. If you haven't already filled out your demographics with the research staff, please click [this link](#) to do so.

You are in the group that gets a detailed anatomy ultrasound in the [first/second] trimester. Based on this, a survey [has been/will be] made available to you about your experience after your detailed anatomy ultrasound. Filling out this survey helps us understand what women like you prefer regarding their ultrasounds. We want to hear from you!

Because you are in the group that gets a detailed anatomy ultrasound in the [first/second] trimester, your next step in the study is to get [an ultrasound to check on the baby/your detailed anatomy ultrasound] between 18 and 22 weeks, which will be scheduled by your doctor. You don't have to do anything—we'll take care of everything, and all your information will be kept confidential.

If you have any concerns about the study or want to withdraw, please email [[contact]](mailto:[contact]). Have a great day!

Sincerely,

[name]  
Principle Investigator, EASE-O

#### Standardized second trimester detailed anatomy survey email (comparison arm after detailed second trimester anatomy scan)

Dear [Name],

I hope you haven't forgotten about EASE-O, a randomized clinical trial to find out when is the best time for a detailed anatomy ultrasound in women with a BMI of 35 or greater. You're almost done with your participation! [If you haven't already filled out your demographics with the research staff, please click [this link](#) to do so.]

You are in the group that gets a detailed anatomy ultrasound in the second trimester. Based on this, you may have already had your detailed anatomy ultrasound, or it might be coming up soon! After your ultrasound, please fill out [this survey](#). Filling out this survey helps us understand what women like you prefer regarding their ultrasounds. We want to hear from you!

This is the last step for you in the study. After this survey, you don't have to do anything—we'll take care of everything, and all your information will be kept confidential.

If you have any concerns about the study or want to withdraw, please email [[contact]](mailto:[contact]). Have a great day!

Sincerely,

[name]  
Principle Investigator, EASE-O

**Standardized second trimester safety ultrasound reminder (intervention arm)**  
Dear [Name],

I hope you haven't forgotten about EASE-O, a randomized clinical trial to find out when is the best time for a detailed anatomy ultrasound in women with a BMI of 35 or greater. You're almost done with your participation! [If you haven't already filled out your demographics with the research staff, please click [this link](#) to do so.]

You are in the group that got a detailed anatomy ultrasound in the first trimester. Even though that was neat, that ultrasounds is still considered experimental (that's why we are researching them)! You deserve to have a complete re-evaluation of your baby's body parts between 18-22 weeks, which is coming up soon.

This safety measure is the last step for you in the study. Afterwards, you don't have to do anything—we'll take care of everything, and all your information will be kept confidential. If you have any concerns about the study or want to withdraw, please email [[contact]](mailto:[contact]). Have a great day!

Sincerely,

[name]  
Principle Investigator, EASE-O

**Withdrawal Email 1 (for intervention arm, withdrawing during her detailed first trimester ultrasound)**

Dear [Name],

We are sorry to see you go! Thank you for considering EASE-O, a randomized clinical trial to find out when is the best time for a detailed anatomy ultrasound in women with a BMI of 35 or greater. This email confirms that you have withdrawn from the study. Your data will not be analyzed and no further data will be collected.

You do not have to do anything further, but we ask that you tell us about your experience during your ultrasound, at [this link](#). Filling out this survey helps us understand what women like you prefer regarding their ultrasounds. We want to hear from you!

Sincerely,

[name]  
Principle Investigator, EASE-O

**Withdrawal Email 2 (for intervention arm, withdrawing after her detailed first trimester ultrasound, before her safety second trimester ultrasound)**

Dear [Name],

We are sorry to see you go! Thank you for participating in EASE-O, a randomized clinical trial to find out when is the best time for a detailed anatomy ultrasound in women

with a BMI of 35 or greater. This email confirms that you have withdrawn from the study. Your data will not be analyzed and no further data will be collected.

You do not have to do anything further, but we encourage you to seek out an ultrasound between 18 and 22 weeks gestational age, if you haven't already gotten one. You did have an ultrasound in the first trimester looking at all the baby's parts, but these ultrasounds are still considered experimental (that's why we are researching them)! You deserve a later ultrasound, it is still recommended and will be covered by your insurance as part of your routine prenatal care.

Sincerely,

[name]  
Principle Investigator, EASE-O

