### **2.4. Primary Outcome**

The primary outcome is the completion rate (number of scans that see all the views listed on pages 7 or 8 divided by total number of scans in that group) for first trimester ultrasounds, compared to the same metrics obtained in second trimester ultrasounds.

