### **3.6. Subject Replacement**

Subjects who withdraw from the study will be replaced.

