trimester ultrasound by the clinical team as part of standard obstetrical care and completes a survey regarding her satisfaction with this technique via email. Research staff will ensure patients have this scan scheduled and completed, as it is part of study procedure. Data about this scan will be recorded in the patient's research record. This scan can be repeated as indicated according to UT's protocol for assessing anatomy.

*c. Final Study Visit:*

The final study visit is denoted by completion of the second trimester gold standard scan (GSS) for patients randomized to the intervention arm, and at the completion of the second trimester anatomy ultrasound for patients randomized to the comparison arm. Participants will continue to be followed through their pregnancy to document the number of ultrasounds required to complete the fetal anatomy evaluation.

*d. Post Study Follow up and Procedures*

Medical records will be reviewed after each study participant's due date to assess whether delivery has occurred and to record delivery outcomes from the medical records, when available. This is chiefly so that a post-natal evaluation can be recorded to confirm or exclude anatomical anomalies. Delivery outcomes are not a primary outcome and request of outside delivery records will not be required for a subject's record to be marked as completely collected.

Adverse outcomes, including discomfort during ultrasound as well as neonatal outcomes, will be recorded in the subject's research record.

*e. Discontinuation Visit and Procedures*

Subjects may withdraw voluntarily from participation in the study at any time. Subjects may also withdraw voluntarily from receiving the study intervention for any reason.

If a patient in the intervention arm withdraws from the study during to her first trimester anatomy ultrasound, she will be asked to complete the survey regarding her experience regardless of the duration of the first trimester ultrasound. She will then undergo her clinically indicated ultrasound (which are not transvaginal).

If a subject in the intervention arm withdraws from the study prior to her second trimester GSS ultrasound (done as "back up" for the intervention), a standard email will be sent to her confirming her withdrawal and encouraging her to seek a second trimester (standard of care) anatomy ultrasound as the anatomy evaluation she had in the first trimester is considered experimental.

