**Withdrawal Email 3 (for comparison arm, withdrawing from study before detailed second trimester ultrasound)**

Dear [Name],

We are sorry to see you go! Thank you for participating in EASE-O, a randomized clinical trial to find out when is the best time for a detailed anatomy ultrasound in women with a BMI of 35 or greater. This email confirms that you have withdrawn from the study. Your data will not be analyzed and no further data will be collected.

You do not have to do anything further, but we encourage you to seek out an ultrasound between 18 and 22 weeks gestational age, if you haven't already gotten one. The ultrasound you got in the first trimester was only to establish the dating of your pregnancy or check on the back of the baby's neck, and didn't look at all the baby's body parts. A detailed ultrasound between 18 and 22 weeks recommended and will be covered by your insurance as part of your routine prenatal care.

Sincerely,

[name]  
Principle Investigator, EASE-O

## APPENDIX 4

[figure not shown]

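### The plan keeps an exam stopped early in the analysis but removes and replaces an intervention woman who withdraws during or after her outcome scan, and no rule says which governs the primary completion rate

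*Combined protocol and SAP*

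**What the plan says.** Five parts of the combined protocol and SAP bear on a woman whose outcome scan is cut short.

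- **Section 2.4** defines the primary outcome as "number of scans that see all the views listed on pages 7 or 8 divided by total number of scans in that group". The denominator is scans, so a scan that was begun belongs in it.
- **Section 7.2** covers a woman who, in discomfort, declines to go on: "the exam will stop and completion will be assessed based on the images obtained before that point".
- **Section 9.2** adopts intention-to-treat and adds: "All randomized subjects will be included in analyses for which they have data".
- **Section 4.3.e** describes a different event, which begins: "If a patient in the intervention arm withdraws from the study during to her first trimester anatomy ultrasound". The same section separately notes: "Subjects may also withdraw voluntarily from receiving the study intervention for any reason". It does not say how the outcome is scored in either case.
- **Appendix 3** supplies three withdrawal emails. Email 1 is for withdrawal during the first trimester scan, and Email 2 for withdrawal after it but before the second trimester scan. Email 3 is for a comparison woman who withdraws before her second trimester scan. All three carry the sentence "Your data will not be analyzed and no further data will be collected". Section 3.6 adds, for both arms: "Subjects who withdraw from the study will be replaced".

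Section 3.4 also excludes from analysis any woman who did not receive a second trimester ultrasound.

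**The concern.** An intervention woman who leaves the study during her first trimester scan has a primary outcome that is at least partly observed, and it will usually be a scan with missing views. Sections 2.4, 7.2 and 9.2 together point to keeping her. Email 1 and Section 3.6 point to removing her and recruiting someone else, who may complete the scan. No passage ranks these rules or tells staff where a stopped exam ends and a study withdrawal begins. That label would be applied by research staff who know the arm and can see that the scan is failing.

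Section 2.2 asks whether the first trimester scan is feasible and how often it is complete. A woman who cannot tolerate it is one of the failures that the trial exists to count. Section 7.2 itself expects discomfort, above all with the transvaginal approach, to be common. Three results are exposed: the primary comparison, the feasibility finding, and the Section 3.5 rule that stops the study if fewer than half of first trimester scans can be completed.

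**Working it through.** **Step 1. When each email applies, relative to that arm's outcome scan.**

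| Template | Arm | Timing | Is the result known? |
|---|---|---|---|
| Email 1 | Intervention | During the outcome scan | Partly, and probably incomplete |
| Email 2 | Intervention | After the outcome scan | Yes |
| Email 3 | Comparison | Before the outcome scan | No |

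Removal under Email 3 cannot depend on a result that does not yet exist. Removal under Email 1 almost always takes out an incomplete scan. Email 2 can remove either result, so it biases the rate only if leaving is related to what the scan showed.

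**Step 2. Inputs.** Section 4.1 lists 19 + 20 + 20 = 59 women per arm. Section 9.1 plans on 70% against 85% completion, a difference of 15 points. Section 9.2 specifies a chi-square test. The documents give no stopping or withdrawal rate, so there is no planned figure to reproduce, and every rate of removal below is an assumption.

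**Step 3. Effect in counts.** Assume 47 of 59 intervention scans are complete, which leaves 12 failures. If *k* of those failures are removed, the rate is 47/(59 − *k*).

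- *k* = 0: 47/59 = 79.7%
- *k* = 1: 47/58 = 81.0%, a gain of 1.4 points
- *k* = 3: 47/56 = 83.9%, a gain of 4.3 points
- *k* = 6: 47/53 = 88.7%, a gain of 9.0 points

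**Step 4. Effect with replacement.** Let *p* be the true completion rate and *d* the share of intervention women whose incomplete scan is removed and replaced. The expected observed rate is *p*/(1 − *d*). With 59 women, *d* = 2%, 5% and 10% correspond to about 1, 3 and 6 women. The last column takes a true 70% in both arms and 59 per arm. It gives the exact binomial probability that the two-sided 5% uncorrected chi-square test is significant in favour of the intervention.

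| *d* | True 70% reads as | True 85% reads as | False positives favouring the intervention |
|---|---|---|---|
| 0 | 70.0% | 85.0% | 2.6% |
| 2% | 0.70/0.98 = 71.4% | 0.85/0.98 = 86.7% | 3.8% |
| 5% | 0.70/0.95 = 73.7% | 0.85/0.95 = 89.5% | 6.7% |
| 10% | 0.70/0.90 = 77.8% | 0.85/0.90 = 94.4% | 16.2% |

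**Step 5. Interim rule.** A true rate of 45%, which is below the 50% threshold, reads as 0.45/0.95 = 47.4% at *d* = 5% and 0.45/0.90 = 50.0% at *d* = 10%. The interim look comes at 59 women, so about 29 or 30 are in the intervention arm. At *d* = 10%, the chance of observing at least 50% rises from 29.3% to 50.0% with 29 scans, and from 35.5% to 57.2% with 30.

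**The case against.** The best defence is that these rules describe different events. Section 7.2 deals with ending an exam, whereas Section 4.3.e and Email 1 deal with leaving the study, and 4.3.e itself separates leaving the study from declining the intervention. This stands. A reader might infer that any woman who stops her first trimester scan is dropped and replaced. The documents do not say so: one who only stops the exam is kept under 7.2. Nor does 7.2 score her incomplete automatically. It scores the images obtained, which is incomplete unless every view had already been seen. What the defence leaves open is the boundary between the two events, and the treatment of a woman who really does withdraw mid-scan although her outcome is partly observed. The limit in 9.2 to women with data does not settle this, because Email 1 promises not to analyse data that exist.

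A reader might also infer that removal affects the intervention arm alone, with no loss on the other side. That is too strong. Withdrawal at any time (3.5) and replacement (3.6) apply to both arms, and Email 3 repeats the promise not to analyse. The survey email to comparison women allows that their scan may already have happened and tells them how to withdraw. What stands is narrower: only the intervention arm has a written procedure for removal during or after the outcome scan.

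The size is open to challenge too. Nothing in the documents shows that more than one woman, or any, would take this route, and the 9-point figure needs half of the 12 assumed failures to leave the study. Finally, the consent form was not in the text available for this review. It may say whether data already collected are kept after withdrawal.

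**Conclusion.** The point holds as an unresolved conflict between rules, with a foreseeable direction of bias. Email 1 and Section 3.6, followed as written, remove and replace women whose outcome scan was probably a failure, contrary to the intention-to-treat commitment in 9.2. Equivalent removal after a result exists is not written out for the comparison arm. Where the removed scans are incomplete, the first trimester completion rate can only move up.

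How far it moves cannot be settled from the documents. One such woman is worth about 1.4 points and three about 4.3 points, on the assumption of 47 complete scans in 59. The effect is modest if the event is rare, but material against a planned difference of 15 points if discomfort leads several women to leave. The documents do not support reading this as a known inflation, as automatic removal of everyone who stops, or as loss confined to one arm.

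**What to change.** 1. State in 9.2 that every randomized woman whose outcome scan was started, in either arm, stays in her arm in the primary analysis and is scored on the images obtained, including when she withdraws during or after that scan.
2. Amend 3.6 so that a replacement may be recruited but never takes the original woman's place in the analysis.
3. Reword Emails 1, 2 and 3 to say that collection of further data stops and that data already obtained are kept as consent allows. Check the consent form for consistency.
4. Reconcile the 3.4 exclusion for no second trimester ultrasound, so that it does not take a woman with a started first trimester scan out of the primary analysis. Without this, a mid-scan withdrawal could still be lost after items 1 to 3.
5. Report withdrawals and any deletion of data by arm, with a sensitivity analysis that counts deleted started scans as incomplete.

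These changes govern analysis only and leave each woman's freedom to stop or withdraw untouched. The cost is wording and an IRB amendment, with no additional patients. The first trimester completion rate may come out slightly less favourable.
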